2.2 Analysis populations

The analysis populations will be defined as follows for this study:

- The ITT population will consist of all subjects that have met all eligibility criteria, undergone successful PTA of the target lesion, and into which the COVERA™ Vascular Covered Stent System is introduced (i.e. the delivery system enters the subject's body).

Subjects who do not receive the study device, but into which the COVERA™ Vascular Covered Stent System was introduced, will be included in the ITT population. Subjects who require additional treatment modalities will be included in the ITT population.

- The Modified ITT (MITT) population will consist of any subjects in the ITT population who are treated with the COVERA™ Vascular Covered Stent (following PTA).
- A Per-Protocol (PP) population may be created if there are subjects who have any major protocol deviations. The PP population will consist of any subjects in the MITT population who do not have any major protocol deviation. The protocol deviations that are considered to have a "major" grade will be defined a priori in the analysis plan.

All analyses including the primary analyses will be primarily based on the MITT population. Key safety analysis will be performed based on ITT population as well. PP analyses may also be performed for the primary endpoints. They will only serve as sensitivity analyses for the primary analyses which are based on the MITT population.

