2.4 Handling of Missing Data

Study endpoints may be missing due to withdrawal of consent, Investigator's decision, LTF and subject death. It is important to minimize missing data by all means and always record the reason for missing. Missing data will be handled as described subsequently.

As a sensitivity analysis, the primary effectiveness and safety endpoints will also be analyzed using survival analysis techniques. In survival analyses, unobserved endpoints are a standard part of the analysis; they are known as "censored observations". As long as the censoring is unrelated to the treatment, this method of handling missing endpoints produces unbiased estimates of the freedom-from-event rates. For both primary endpoints, the reason for the censoring of all subjects with missing endpoints will be reported. If there is any indication that the censoring is related to the study intervention, a worst-case analysis may be performed for each primary endpoint, in addition to the standard analysis. In a worst-case analysis, an event will be assumed to have occurred at the time the subject was censored for all such subjects.

In addition, regardless of whether missing data are related to the study intervention, a tipping-point analysis will also be performed, in which assumptions about missing data are varied from worst-case to best-case to examine at what point the missing data would alter the results of the analysis.

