2.5 Sample Size Estimation

The sample size calculation assumes the following:

- 1) Primary Effectiveness Endpoint – TLPP at 6 months performance goal.
 - Assumptions:
 - The COVERA™ Vascular Covered Stent composite freedom from event rate is estimated at 55%;
 - The PG is set at 40%;
 - Attrition (drop-out) rate (by 6 months) = 15%;
 - The Type 1 error, $\alpha = 0.05$ (one-sided); and
 - The Type 2 error, $\beta = 0.10$ (Power = $1 - \beta = 90\%$).
 - Sample Size:
 - 109 treated subjects [93 evaluable] will give 90% power with one-sided type I error =0.05.
- 2) Primary Safety Endpoint – Safety at 30 days:
 - Assumptions:
 - The primary safety rate through 30 days in the study device treated subjects is 98%;
 - The PG is set at 88%;

- Attrition rate (by day 30) = 5%; and
- The Type 1 error, $\alpha = 0.05$ (one-sided).
- Sample Size:
 - 109 treated subjects [104 evaluable] will give 99% power with one-sided type I error =0.05.

Hence, the sample size of 109 subjects will provide approximately $(99\%)*(90\%)=89\%$ power for the both primary effectiveness and primary safety endpoint.

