2.7 Evaluation of Secondary Endpoints

The following secondary endpoints will be summarized with descriptive statistics (without formal statistical hypothesis testing) using the MITT population. For categorical variables, summary statistics will include frequency counts and percentages. For continuous variables, summary statistics will include mean, standard deviation, minimum, median, and maximum.

- TLPP through 30 days, 90 days, 12 months, 18 months, and 24 months.
- ACPP through 30 days, 90 days, 6 months, 12 months, 18 months, and 24 months.
- Rate of device and procedure related AEs involving the AV access circuit through 90 days, 6 months, 12 months, 18 months, and 24 months.

- Total Number of AV Access Circuit Reinterventions through 30 days, 90 days, 6 months, 12 months, 18 months, and 24 months.
- Total Number of Target Lesion Reinterventions through 30 days, 90 days, 6 months, 12 months, 18 months, and 24 months.
- IPF evaluated at 30 days, 90 days, 6 months, 12 months, 18 months, and 24 months follow-up.
- IPF-T evaluated at 30 days, 90 days, 6 months, 12 months, 18 months, and 24 months.
- Secondary Patency evaluated through 30 days, 90 days, 6 months, 12 months, 18 months, and 24 months.
- Acute Technical Success.
- Acute Procedure Success (Anatomic and Clinical Success).

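### Reintervention totals through 24 months are summarized without time at risk: drop-out biases a mean over all treated subjects low, and access loss or death leaves the count open to misreading

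*Combined protocol and SAP*

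**What the plan says.** Section 2.7 of the combined protocol and SAP lists two reintervention endpoints at six cumulative time points: "Total Number of AV Access Circuit Reinterventions through 30 days, 90 days, 6 months, 12 months, 18 months, and 24 months" and "Total Number of Target Lesion Reinterventions through 30 days, 90 days, 6 months, 12 months, 18 months, and 24 months". Like the other secondary endpoints, they are to be "summarized with descriptive statistics (without formal statistical hypothesis testing) using the MITT population". The method for a numerical variable is this: "For continuous variables, summary statistics will include mean, standard deviation, minimum, median, and maximum". Section 2.7 gives no time-at-risk denominator, no censoring rule, and no rule for death or loss of the access.

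Section 2.2 defines MITT as "any subjects in the ITT population who are treated with the COVERA™ Vascular Covered Stent (following PTA"). Length of follow-up is not a condition, so a subject last seen at month 3 belongs to MITT at month 24.

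Section 2.4 acknowledges incomplete follow-up: "Study endpoints may be missing due to withdrawal of consent, Investigator's decision, LTF and subject death". Its remedy is that "the primary effectiveness and safety endpoints will also be analyzed using survival analysis techniques", and its worst-case analysis is also for the primary endpoints. The tipping-point paragraph gives no method for a recurrent-event count.

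Section 2.5 shows the scale of loss that the sponsor expects: "Attrition (drop-out) rate (by 6 months) = 15" percent. Follow-up runs to 24 months (Section 1).

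**The concern.** A count of repeated events depends on how long each subject was observed and could have had an event. There are two separate problems.

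- **Drop-out.** After withdrawal or loss to follow-up, reinterventions can still occur but are not recorded. The recorded count looks complete, so nothing marks it as missing. A mean over all treated subjects is then too low, and increasingly so at later time points.
- **Death or access loss.** No further reintervention of that circuit is possible. The recorded count is true, but it does not distinguish a circuit that needed little maintenance from one that no longer existed.

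At stake is how the 24-month results are read. In a single-arm study no control group with similar losses puts the counts in context, so a low figure is likely to be taken at face value.

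**Working it through.** **Inputs from the documents**
- 109 treated subjects, 93 evaluable, 15% attrition by 6 months (Section 2.5).
- Time points of 30 days, 90 days, and 6, 12, 18 and 24 months (Section 2.7).
- No reintervention, death or access-loss rate is given, so the plan has no figure for these endpoints to reproduce. The attrition input does reproduce: 109 × 0.85 = 92.65, which rounds to the stated 93.

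**Assumptions for illustration**
- The loss fraction d per 6 months continues at a constant hazard to 24 months.
- The reintervention rate is constant while a subject is at risk.
- All of the loss is drop-out, and it is unrelated to the need for reintervention.
- The mean is taken over all treated subjects.

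**Formulas**
- Hazard per month: h = −ln(1 − d)/6.
- Mean fraction of nominal time T that is observed: f(T) = (1 − e^(−hT))/(hT).
- Shortfall in the mean count: 1 − f(T).

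**Result for d = 15%**, where h = 0.1625/6 = 0.0271 per month:

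| Time point | Still followed | Observed fraction f | Shortfall |
|---|---|---|---|
| 30 days | 97.4% | 0.987 | 1.3% |
| 6 months | 85.0% | 0.150/0.1625 = 0.923 | 7.7% |
| 12 months | 72.2% | 0.2775/0.3250 = 0.854 | 14.6% |
| 24 months | 52.2% | 0.4780/0.6501 = 0.735 | 26.5% |

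At 24 months 0.522 × 109 ≈ 57 subjects are still followed. Mean observed time is 0.735 × 2 = 1.47 years. A true rate of 1.0 per year would therefore appear as a mean of 1.47 reinterventions per treated subject, against 2.0 with full observation. Total events divided by total time at risk returns 1.0 per year.

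**Range at 24 months**
- d = 5%: f = 0.904, shortfall about 10%.
- d = 25%: f = 0.594, shortfall about 41%.

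**Access loss or death, by example**
- Circuit A is lost at month 3 after one reintervention: count 1, rate 1/0.25 = 4.0 per year at risk.
- Circuit B works for 24 months with three: count 3, rate 3/2 = 1.5 per year at risk.

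Both counts are correct, yet the two measures order the circuits oppositely. A mean cumulative count with access loss as a terminal event would still leave A at 1. It corrects for drop-out but does not by itself resolve this case.

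**The case against.** **For death and access loss the raw count is not an error.** This stands. If follow-up is otherwise complete, the raw mean equals a mean cumulative count with terminal events. A rate per access-year is a different quantity, which Section 2.7 does not claim to report. A reader might infer that access loss and death bias the count low. The documents do not support that; they support only that the count is hard to interpret without those losses beside it.

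**The percentages do not measure access loss.** This also stands. They extend a sample-size assumption for the primary effectiveness endpoint from 6 to 24 months. Section 2.5 calls it drop-out, but Section 2.4 counts death among the reasons for missing endpoints. If the 15% includes deaths, that part produces no unseen events and the drop-out bias is smaller.

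**The denominator is not stated.** Section 2.7 does not say whether the total is for the cohort or per subject, or whether it covers all treated subjects or only those followed to each time point. With the latter, the calculated shortfall does not arise in this form. A reader might infer that the plan chose a biased denominator; more exactly, a mean over all of MITT is the natural reading of an unspecified one. A cohort total ignores exposure just the same.

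**Other endpoints may help.** Secondary Patency, IPF and IPF-T are listed at the same six time points and may show time or access loss. The supplied text neither defines them nor links them to the counts, so they can be neither credited as a remedy nor dismissed.

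**The endpoints are descriptive.** They carry no hypothesis test and no performance goal, and no planned analysis ranks subjects by count. That limits the importance of the point without removing it.

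**Conclusion.** The point holds in limited form. Read as a mean over all treated subjects, the planned summary is biased low through reinterventions unseen after drop-out. The bias is trivial at 30 days and grows to about 26% at 24 months if the plan's 6-month attrition continues (about 10% to 41% over the range examined). The direction follows from the method. The size rests on assumed constant loss and reintervention rates, and on all the loss being drop-out. Separately, the counts cannot be read as maintenance burden unless access losses and deaths are shown with them.

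A reader might also infer a threat to the study's main conclusions. There is none: both primary tests, their error rates and the 109 subjects are unaffected.

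**What to change.** In Section 2.7:

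1. Report both reintervention endpoints as events per access-year at risk, with time at risk ending at loss of secondary patency, death, withdrawal or last contact.
2. Beside each time point, show the number at risk, the circuits lost and the deaths.
3. Optionally, add a mean cumulative count that censors at drop-out and treats death and access loss as terminal. This corrects the drop-out bias but does not replace items 1 and 2.
4. Keep the raw totals as a listing, and state whether each is for the cohort or per subject.

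The cost is SAP wording and one extra table, plus a figure if the curve is added. The dates of access loss and last contact should largely be needed for Secondary Patency already, although the supplied text does not confirm this. The reported burden will look somewhat higher than the raw totals suggest.

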2.8 Exploratory Analyses and Subgroup Analyses

The primary endpoints will be explored in subgroups:

- Gender;
- Geography;
- Lesion characteristics; and
- Presence of secondary lesion(s).

The information is intended to be reported in the device's labeling and will be summarized using descriptive statistics.

2.9 Interim Analysis

An interim analysis will be performed when all subjects have completed the 6-month follow-up visit.
